11.2. Baseline Data

- Unless otherwise specified, baseline is the last observation before the first study drug administration.
- The baseline lesion assessment is considered to be the one within 72 hours following Ad-RTS-hIL-12 administration.
- If the schedule of events includes a baseline value (i.e. Day -7) lab just before study drug administration) that is not collected as planned for any reason, then the data collected for the variable known to be the last observation before the first dose of study drug will serve as the baseline value.
- In addition, the relevant section for each endpoint will describe the baseline values of subjects recorded as taken before study treatment according to schedule along with subjects for whom measurements should have been taken before study treatment but for whom those measurements were taken after study dosing was received.

11.3. Change from baseline

- Change from baseline is performed for Serum Chemistry, Hematology, Urinalysis, Vital Signs, ECG Results and the Karnofsky Performance Status (KPS) Score.

11.4. Measurements Collected Excluded from Predefined Analysis

- Populations or extra measurements that were repeated or obtained based on unscheduled visits may not be included in summary tables unless specified.
- Regardless of data inclusion for any analysis
 - Subject Listings will present all available data received in the electronic CRF (eCRF)
 - Where applicable subject listings will also present all final data received from data sources for which data external to the eCRF were captured for which data transfer agreement specifications were established.

11.5. Derived and Computed Variables

- Day 0 corresponds to the date of Ad-RTS-hIL-12 administration.
- Then more generally, Day n represents the elapsed number of days from Day 0, inclusive.
- Day n = Date of assessment – Date of Day 0.
- Unless otherwise specified, the timing of all study-related events, assessments, and interventions will be calculated relative to Day 0. Day -1 will be the day before Day 0, and in general, negative days will be measured backwards starting from Day -1.
- Day -7 corresponds to the first dosing date of subjects treated with Ad-RTS-hIL-12 and cemiplimab.

- 1 year = 365.25 days. Year is calculated as (days / 365.25) and will be rounded up to 1 significant digit for purposes of presentation.
- 1 month = 30.4375 days. Month is calculated as (days / 30.4375) and will be rounded up to 1 significant digit for purposes of presentation.
- Age will be calculated in years relative to the date of informed consent based on the following SAS statement: Age = floor ((intck('month', date of birth, date of informed consent) – (day (informed consent) < day (date of birth))) / 12 (Check with LLX and Ziopharm Programming)
- 1 pound = 0.454 kg
- 1 inch = 2.54 cm
- Pregnancy test data will be listed only.

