1. INTRODUCTION

This Statistical Analysis Plan (SAP) describes the proposed statistical analyses in concert with Ziopharm Protocol ATI001-204 Amendment 2 entitled: A Phase II Study of Ad-RTS-hIL-12 + Veledimex in Combination with Cemiplimab(Libtayo®) in Subjects with Recurrent or Progressive Glioblastoma.

Importantly, and where applicable, all references pertaining to the protocol in this SAP are meant to imply “contains a more detailed explanation of the statistical analyses” in the Protocol ATI001-204 Amendment 2. It includes additional and sometimes technical discussion for implementing statistical procedures along with the assumptions and data handling rules of how an analysis is performed.

Glioblastomas are by far the most frequent malignant glioma and are associated with a particularly aggressive course and dismal prognosis ([Lieberman, 2017](#)). Standard of care treatment for glioblastomas is based on surgical resection with the intent to remove as much of the tumor as is feasible ([Fernandes et al., 2017](#); [Paolillo, Boselli, & Schinelli, 2018](#)). Resection is then followed by radiotherapy and concomitant adjuvant temozolomide. However, such aggressive treatment is associated with only modest improvements in survival. Newly diagnosed glioblastoma subjects have a median overall survival (OS) of 12 to 15 months ([Ahmed, Oborski, Hwang, Lieberman, & Mountz, 2014](#)) and 2-year OS rate of up to 27% ([Omuro & DeAngelis, 2013](#)), while OS in subjects that have failed TMZ and bevacizumab, or equivalent salvage chemotherapy, is reported as being as short as 3 to 5 months ([Iwamoto et al., 2009](#); [Omuro & DeAngelis, 2013](#)). To date, no salvage treatment has been validated by Phase III data for recurrent or progressive glioblastoma. For subjects with recurrent glioblastoma, the median OS is 6 to 7 months ([Omuro & DeAngelis, 2013](#)), and median progression-free survival (PFS) is 2 to 3 months.

Please refer to the finalized protocol and its amendments to follow the plan as originally envisioned.

Protocol Chronology

- Amendment 2: 08Jan2020
- Amendment 1: 09May2019
- Original: 07Feb2019

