8. EFFICACY ANALYSIS

No formal hypothesis testing will be performed for primary and secondary endpoints. Estimates of the single arm will be determined and will be compared numerically with historical control estimates, wherever applicable.

Observed data will be presented over all study centers. No imputation of values for missing data will be performed.

In general, all estimates will be calculated considering two-sided 5% level of significance. No adjustments for covariates will be made.

- See [Section 10](#) of this document for all changes to originally preplanned efficacy analyses.

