8.1. Primary Efficacy Endpoint

The primary endpoint for evaluation of efficacy is the OS hazard rate which is performed by estimating the hazard rate based on the accrual and follow-up of all treated subjects. Subjects will be followed from the first date of treatment up to 2 years for overall survival.

OS is defined as the duration of time from the first dose of study drug (i.e., cemiplimab at Day - 7) to the date of death from any cause. Censoring will be considered as below:

- Subjects who discontinue study will be censored at date of discontinuation.
- Subjects who are lost to follow-up will be censored at last follow-up contact date.
- If the subject has not died, the subject is censored if still alive up to 2 years from the first dose of study drug received.

All summaries and analyses for the primary efficacy endpoint will be based on per-protocol population.

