8.2. Primary Analysis for OS

The primary analysis for estimating the hazard rate for the time to OS denoted as the function $S(t)$ will be performed on the PP population using the Kaplan Meier (KM) Product-Limit estimation method. A secondary analysis will also be implemented for the FAS. Using the KM method:

- The median survival time along with the 95% Confidence Interval (CI) will be constructed.
- The 25Th and 75th quartile of survival time will also be provided supplemented by the Kaplan-Meier plot of OS.

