11.6. Continuous Variables

- Summary statistics will be provided for continuous variables (e.g., age).
- Unless otherwise stated, summary statistics will report:
 - The number of subjects with a non-missing value of the variable (n), mean, standard deviation, median, minimum, and maximum.
 - The same number of decimal places as in the raw data will be presented when reporting minimum and maximum
 - One more decimal place than in the raw data will be presented when reporting mean and median
 - Two more decimal places than in the raw data will be presented when reporting standard deviation.

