13. APPENDICES

APPENDIX 1: ORIGINAL ATI001-204 TLFS

APPENDIX 2: REVISED ATI001-204 TLFS

Table/Figure Number	Table Title	Population	Tab Name	
Table 14.1.1	Subject Disposition	All Subjects	Disp	
Table 14.1.2	Protocol Deviations	Full Analysis Population	Dev	
Table 14.1.3.1	Demography	Full Analysis Population	Demo	
Table 14.1.3.2	Baseline Characteristics	Full Analysis Population	BasChar	
Table 14.1.4	Medical History	Full Analysis Population	Mhx	
Table 14.1.5	High Grade Glioma Diagnosis	Full Analysis Population	Diagh	
Table 14.1.6	Prior Cancer Treatments	Full Analysis Population	Canhist	
Table 14.1.7	Previous Medications	Full Analysis Population	Meds	
Table 14.1.8	Concomitant Medications	Full Analysis Population	Meds	
Table 14.2	Best Overall Response	Per Protocol Population	BOR	
Table 14.2.1	Best Overall Response Concordance	Per Protocol Population	BORC	
Table 14.2.1.1	Objective Response Rate	Per Protocol Population	ORR	
Table 14.2.1.2	95% Confidence Intervals for Overall Response	Per Protocol Population	ORRci	
Table 14.2.2	Progression Free Survival	Per Protocol Population	PFS	Not required at this time
Table 14.2.3	Time to Overall Survival in Months	Per Protocol Population	OS	
Table 14.2.3.1	OS CI 20	Per Protocol Population	OSGAT	

Table 14.3.1.1	Overall TEAEs Summary	Full Analysis Population	AEoverall	
Table 14.3.1.2	Treatment Emergent Adverse Events by System Organ Class and Preferred Term	Full Analysis Population	AEs	
Table 14.3.1.3	Treatment-Related Adverse Events by System Organ Class and Preferred Term	Full Analysis Population	AEs	
Table 14.3.1.4	Adverse Events Leading to Study Discontinuation by System Organ Class and Preferred Term	Full Analysis Population	AEs	
Table 14.3.1.5	Adverse Events Leading to Discontinuation of Study Medication by System Organ Class and Preferred Term	Full Analysis Population	AEs	
Table 14.3.1.6	Adverse Events Leading to Interruption of Study Medication by System Organ Class and Preferred Term	Full Analysis Population	AEs	
Table 14.3.1.7	Adverse Events Leading to Dose Reduction of Study Medication by System Organ Class and Preferred Term	Full Analysis Population	AEs	
Table 14.3.1.8	Adverse Events Leading to Death by System Organ Class and Preferred Term	Full Analysis Population	AEs	

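### SAP 11.5 rounds months and years up to one significant digit for display; as written, the rule can raise a displayed survival time but never lower it

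*SAP*

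**What the plan says.** SAP Section 11.5 sets the conversion from days to longer units. For months: "Month is calculated as (days / 30.4375) and will be rounded up to 1 significant digit for purposes of presentation". For years: "Year is calculated as (days / 365.25) and will be rounded up to 1 significant digit for purposes of presentation". Neither sentence names an endpoint, and both limit the rounding to presentation.

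The parts of the SAP that bring OS within reach of the rule are these:

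- Section 8.1 fixes the time horizon: "Subjects will be followed from the first date of treatment up to 2 years for overall survival".
- Section 8.2 makes the Kaplan-Meier median the main summary: "The median survival time along with the 95% Confidence Interval (CI) will be constructed". The 25th and 75th percentiles are to be given as well.
- The list of tables in Appendix 2 includes Table 14.2.3, "Time to Overall Survival in Months", for the per protocol population.
- Section 8 rules out formal hypothesis tests for the primary and secondary endpoints and says: "Estimates of the single arm will be determined and will be compared numerically with historical control estimates, wherever applicable".

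On precision in general, Section 11.6 says: "One more decimal place than in the raw data will be presented when reporting mean and median". Section 4.6 has a similar rule. Both are defaults that give way where something else is specified. Section 11.7 asks for percentages to one decimal place.

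**The concern.** Two features of the sentence in 11.5 are wrong. One significant digit is not one decimal place: for any time above 10 months it keeps only the tens. And rounding up is one-directional at any precision, so errors do not average out across displayed values.

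For a survival time, up means longer. The OS result of this single-arm trial is to be read beside historical estimates, with no formal test. Those estimates come from outside and are not passed through this rule, so any display error falls on the trial's side only. Section 10.2 also drops the parametric OS estimate and the OS rates at fixed timepoints from the final analysis, so the Kaplan-Meier summary in months is what a reader will mostly look at.

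**Working it through.** **Inputs.** Conversion factors 30.4375 and 365.25 and the rounding rule (SAP 11.5); two-year follow-up (SAP 8.1); 12.7 months, the median OS in the sponsor's Phase I 20 mg cohort (Protocol 6.1), as an illustration and not a result of this trial. The 6.2 months is a made-up example.

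**Step 1. The conversion factor.** 365.25 / 12 = 30.4375. The plan's figure is reproduced exactly; only the rounding is at issue.

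**Step 2. The rule as written.** With m = days / 30.4375 and k the power of ten of the leading digit, the displayed value is 10^k × ceiling(m / 10^k).

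- 12.7 months: 10 × ceiling(1.27) = 20, and 20 / 12.7 − 1 = 57% too high.
- 6.2 months: ceiling(6.2) = 7, and 7 / 6.2 − 1 = 13% too high.
- 24 months (730.5 days): 10 × ceiling(2.4) = 30, and 30 / 24 − 1 = 25% too high. This is longer than anyone is followed.
- Exactly 6 months: ceiling(6) = 6, unchanged.

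The year rule behaves the same way: 387 days / 365.25 = 1.06 years, displayed as 2.

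**Step 3. The alternative readings.** Four readings were applied to every whole-day time from 1 to 731 days. Errors are displayed minus true value, in months.

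| Reading | 6.2 | 387 days (12.71) | 24 | Smallest error | Largest error | Mean error |
|---|---|---|---|---|---|---|
| Up, 1 significant digit (literal) | 7 | 20 | 30 | above 0 | +10.0 | +3.6 |
| Nearest, 1 significant digit | 6 | 10 | 20 | −5.0 | +5.0 | −0.3 |
| Up, 1 decimal place | 6.2 | 12.8 | 24.0 | 0 | +0.10 | +0.05 |
| Nearest, 1 decimal place | 6.2 | 12.7 | 24.0 | −0.05 | +0.05 | 0.00 |

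Under the literal rule all 731 times are overstated, and from one month upward the only values that can appear are 2 to 10, 20 and 30. Rounding up to one decimal place overstates 730 of the 731 and leaves one exact. Ordinary rounding to one decimal place has no direction.

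**Step 4. The residual error against sampling error.** Assume exponential survival, so that the standard error of the log median is 1/√(deaths), and take an illustrative median of 6.5 months. The number of deaths is also an assumption.

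- 15 deaths: 6.5 × exp(±1.96 × 0.258) gives 3.9 to 10.8 months.
- 25 deaths: 6.5 × exp(±1.96 × 0.200) gives 4.4 to 9.6 months.
- 36 deaths: 6.5 × exp(±1.96 × 0.167) gives 4.7 to 9.0 months.

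A display error of at most 0.1 month is small beside any of these intervals.

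**The case against.** The strongest reply is that nobody would program the literal rule. It shows a subject censored at two years as 30 months, and elsewhere the SAP works in decimal places (4.7, 11.6, 11.7), so one decimal place is the evident intent. On that reading what is left is at most 0.1 month, which could not change a judgement about OS. This largely stands and is why the point is minor. It does not rescue the sentence: 11.5 is operative text, the precision rules in 4.6 and 11.6 are defaults that do not clearly override a specific rule, and the word for up remains wrong even if decimal places were meant.

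The second reply is that use for OS is inferred. Section 11.5 is general, Sections 8.1 and 8.2 give no rounding rule, and the display formats sit in a separate shells spreadsheet of which Section 11.10 reproduces only the contents lists. The OS shell may set its own precision. This stands as a limit on certainty.

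The third reply concerns the comparator. A reader might infer that the rule distorts a formal comparison with the introduction's figure: "For subjects with recurrent glioblastoma, the median OS is 6 to 7 months". The documents do not support that. They give this as background and do not name it as the control value; the primary endpoint text in SAP 3.3.1 speaks of comparing the hazard rate, which a display rule for months does not alter. What remains is that a median in months will be shown and read beside outside figures.

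**Conclusion.** Wrong as written; a minor wording correction to an operative rule. The size depends on the reading: up to 10 months too high if followed literally within the two-year follow-up, and 0 to 0.1 month too high if one decimal place was meant, which is the likelier intent.

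The conclusion assumes that Table 14.2.3 follows 11.5, since no other month-display rule appears in the SAP text.

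Three stronger readings should not be drawn:

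- That the OS analysis is biased. The rounding is for presentation, so the Kaplan-Meier calculation, event counts and censoring are unaffected.
- That the rule always favours the treatment. A value already at one significant digit does not move, so the exact statement is that the rule leaves a displayed time unchanged or raises it.
- That 11.5 flatly contradicts 4.6 and 11.6. Those are defaults that yield to a specific rule; the three are untidy together and should be aligned.

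**What to change.** In both sentences of SAP 11.5 (months and years), replace the rounding instruction with: *rounded to 1 decimal place (ordinary rounding) for presentation only; unrounded values are used in analysis*. Check that the shell for Table 14.2.3 uses the same display.

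The cost is a few words in two sentences. No data, design or analysis changes. The largest display error becomes 0.05 month in either direction.

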11.6. Continuous Variables

- Summary statistics will be provided for continuous variables (e.g., age).
- Unless otherwise stated, summary statistics will report:
 - The number of subjects with a non-missing value of the variable (n), mean, standard deviation, median, minimum, and maximum.
 - The same number of decimal places as in the raw data will be presented when reporting minimum and maximum
 - One more decimal place than in the raw data will be presented when reporting mean and median
 - Two more decimal places than in the raw data will be presented when reporting standard deviation.

11.7. Categorical Variables

- Frequency counts will be provided for categorical variables (e.g., gender).
- Unless otherwise stated, frequency statistics will consist of the number of subjects with a response in a particular category and the percentage of the total number of subjects in that column.
- Unless otherwise stated, missing responses will be included in both the display and in the calculation of percentages (i.e., they will be included in the denominator).
- Percentages will be rounded to one decimal place.
- Percentages equal to 100 will be presented as 100% and percentages will not be presented for zero frequencies.

11.8. Visit Windows Derived and Computed Variables Observed Cases and Last Observation Carried Forward, Missing Data and Outliers

- The statistical analysis planned for this study will be performed according to the actual visit dates and times and do not require the calculation of visit windows.
- However, for analyses that require a particular visit as planned, measurements included in that visit must have occurred during the acceptable window defined for the visit in the protocol, unless otherwise specified in this plan.
- As needed, visit windows will also be created for analysis, to include data collected at unscheduled visits.
- Visit windows will apply to all treatment arms.
 - When multiple visits occur within the same window, the visit closest to the target visit day will be selected.
 - When two visits are equidistant from the target day, the visit occurring latest in the window will be used for analysis.

11.9. Statistical Programming Conventions and Considerations

- SAS version 9.4 or higher will be utilized for all data analyses, summary tables, subject listings and figures.
- Derived datasets are also created using (SAS®) software unless specified otherwise.
- The definition of all derived variables and decodes for coded data must appear in the notes.
- Due to space limitations, tables and listings may require a page of notes as a one-time preface to the output.
- In general, summary tables and listings (e.g., post text tables and individual subject data listings) include a “footer” providing explanatory notes that indicate at a minimum:
 - Date of data extraction
 - Date of output generation
 - SAS complete program name, and path where it is stored including the path that generates the output
 - Any other output specific details that require further elaboration (e.g. CRF pages from which the data were obtained)
 - Post text tables also include reference(s) to the subject data listing(s) that supports the summary data. The data extraction date links the output to the archived database that is locked to ensure the replication of the results.

- In general, the listings should be sorted and presented by treatment assignment, investigational site, and subject number. Treatment assignment and site can appear in the banner of the listing.
 - From left to right, the subject number, visit number, visit date, and relative day should appear.
 - When applicable, the data management tools and methods used in the processing of the data should be mentioned. The SOP dictating the data storage, data transfer, and data cleaning process should be stated.

11.10. Appendices to Distinguish Between Original and Revised ATI001-204 for TLF's

Statistical considerations were implemented in support of producing an abbreviated study report which led to a modification to the originally planned TLF specifications.

The modifications to the originally planned TLF specifications are described in the excel spreadsheet, “ATI001-204 Final TLF Shells”.

- The Table of Contents (first tab of spreadsheet) describing the “Original ATI001-204 TLFs” has been extracted from the spreadsheet and is displayed in Appendix 1.
- The Table of Contents (second tab of spreadsheet) describing the “Revised ATI001-204 TLFs” has been extracted from the spreadsheet and is displayed in Appendix 2.

13. APPENDICES

APPENDIX 1: ORIGINAL ATI001-204 TLFS

APPENDIX 2: REVISED ATI001-204 TLFS

Table/Figure Number	Table Title	Population	Tab Name	
Table 14.1.1	Subject Disposition	All Subjects	Disp	
Table 14.1.2	Protocol Deviations	Full Analysis Population	Dev	
Table 14.1.3.1	Demography	Full Analysis Population	Demo	
Table 14.1.3.2	Baseline Characteristics	Full Analysis Population	BasChar	
Table 14.1.4	Medical History	Full Analysis Population	Mhx	
Table 14.1.5	High Grade Glioma Diagnosis	Full Analysis Population	Diagh	
Table 14.1.6	Prior Cancer Treatments	Full Analysis Population	Canhist	
Table 14.1.7	Previous Medications	Full Analysis Population	Meds	
Table 14.1.8	Concomitant Medications	Full Analysis Population	Meds	
Table 14.2	Best Overall Response	Per Protocol Population	BOR	
Table 14.2.1	Best Overall Response Concordance	Per Protocol Population	BORC	
Table 14.2.1.1	Objective Response Rate	Per Protocol Population	ORR	
Table 14.2.1.2	95% Confidence Intervals for Overall Response	Per Protocol Population	ORRci	
Table 14.2.2	Progression Free Survival	Per Protocol Population	PFS	Not required at this time
Table 14.2.3	Time to Overall Survival in Months	Per Protocol Population	OS	
Table 14.2.3.1	OS CI 20	Per Protocol Population	OSGAT	

Table 14.3.1.1	Overall TEAEs Summary	Full Analysis Population	AEoverall	
Table 14.3.1.2	Treatment Emergent Adverse Events by System Organ Class and Preferred Term	Full Analysis Population	AEs	
Table 14.3.1.3	Treatment-Related Adverse Events by System Organ Class and Preferred Term	Full Analysis Population	AEs	
Table 14.3.1.4	Adverse Events Leading to Study Discontinuation by System Organ Class and Preferred Term	Full Analysis Population	AEs	
Table 14.3.1.5	Adverse Events Leading to Discontinuation of Study Medication by System Organ Class and Preferred Term	Full Analysis Population	AEs	
Table 14.3.1.6	Adverse Events Leading to Interruption of Study Medication by System Organ Class and Preferred Term	Full Analysis Population	AEs	
Table 14.3.1.7	Adverse Events Leading to Dose Reduction of Study Medication by System Organ Class and Preferred Term	Full Analysis Population	AEs	
Table 14.3.1.8	Adverse Events Leading to Death by System Organ Class and Preferred Term	Full Analysis Population	AEs	
Table 14.3.1.9	Treatment Emergent Adverse Events by System Organ Class, Preferred Term and Severity	Full Analysis Population	AEs	
Table 14.3.1.10	Treatment Emergent Adverse Events by System Organ Class, Preferred Term and Severity with CTCAE Toxicity Grade ≥ 3	Full Analysis Population	AESev	
Table 14.3.1.11	Serious Adverse Events by System Organ Class and Preferred Term	Full Analysis Population	AESev	
Table 14.3.1.12	Treatment Emergent Adverse Events by Preferred Term in Decreasing Frequency	Full Analysis Population	AEPT	
Table 14.3.1.13	Treatment-Related Treatment Emergent Adverse Events by Preferred Term in Decreasing Frequency	Full Analysis Population	AEPT	
Table 14.3.4.1	Listing of Abnormal Laboratory Values		Sig_lab	
Table 14.3.4.2	Listing of Clinically Significant Laboratory Values		Sig_lab	
Table 14.3.5.1	Ad-RTS-hIL-12 Injections	Full Analysis Population	Exp1	
Table 14.3.5.2	Veledimex Exposure	Full Analysis Population	Exp2	
Table 14.3.5.3	Cemipluma Exposure	Full Analysis Population	Exp3	
Table 14.3.6.1	Summary of Serum Chemistry Results	Full Analysis Population	Lab	
Table 14.3.6.2	Clinical Significance of Serum Chemistry Results	Full Analysis Population	Lab2	
Table 14.3.6.3	Summary of Hematology Results	Full Analysis Population	Lab	
Table 14.3.6.4	Clinical Significance of Hematology Results	Full Analysis Population	Lab2	
Table 14.3.6.5	Summary of Coagulation Results	Full Analysis Population	Lab	
Table 14.3.6.6	Clinical Significance of Coagulation Results	Full Analysis Population	Lab2	

Table 14.3.6.7	Summary of Urinalysis Results	Full Analysis Population	Lab	
Table 14.3.6.8	Clinical Significance of Urinalysis Results	Full Analysis Population	Lab2	
Table 14.3.7	Summary of KPS	Full Analysis Population	KPS	
Table 14.3.8	Summary of Vital Signs	Full Analysis Population	Vitals	
Table 14.3.9	Summary of Weight	Full Analysis Population	Weight	
Table 14.3.10	Targeted Neurological Exam	Full Analysis Population	Neuro	
Table 14.3.11	ECG Findings	Full Analysis Population	ECG1	
Table 14.3.12	Summary of ECG Results	Full Analysis Population	ECG2	
Table 14.3.13	Dose Limiting Toxicities	Per Protocol Population	DLT	
Figure 14.2.3	Kaplan Meier plot of Progression Free Survival by Veledimex Dose			
Figure 14.2.4	Kaplan Meier plot of Overall Survival by Veledimex Dose			
Figure 14.2.5	Kaplan Meier plot of Progression Free Survival by Group			
Figure 14.2.6	Kaplan Meier plot of Overall Survival by Group			
Figure 14.2.7	Forest Plot	Per Protocol Population	FPLT	
Listing 16.2.1	Subject Disposition	Full Analysis Population	L Disp	
Listing 16.2.3.1	Eligibility	Full Analysis Population	L Elig	
Listing 16.2.3.2	Subject Population	Full Analysis Population	L Pop	
Listing 16.2.2	Protocol Deviations	Full Analysis Population	L Dev	
Listing 16.2.4.1	Demography and Baseline Characteristics	Full Analysis Population	L Demo	
Listing 16.2.4.2	Medical and Surgical History	Full Analysis Population	L Mhx	
Listing 16.2.4.3	High Grade Glioma Diagnosis	Full Analysis Population	L Hgg	
Listing 16.2.4.4	Prior Cancer Treatment	Full Analysis Population	L PriCnt	
Listing 16.2.4.5	Previous Medications	Full Analysis Population	L Conn	
Listing 16.2.4.6	Concomitant Medications	Full Analysis Population	L Conn	
Listing 16.2.4.7	Corticosteroid Dosage	Full Analysis Population	L CDD	
Listing 16.2.4.8	Post Treatment Anti-Cancer Therapy	Full Analysis Population	L PostCnt	
Listing 16.2.4.9	Concurrent Medical Procedures	Full Analysis Population	L Npmed	
Listing 16.2.5.1	Ad-RTS-hIL-12 Injection	Full Analysis Population	L DS1	
Listing 16.2.5.2	Veledimex Capsule Diary	Full Analysis Population	L DS2	
Listing 16.2.5.3	Veledimex Dose Modification	Full Analysis Population	L DS3	
Listing 16.2.6.1	Pre-Baseline Lesion Assessment	Full Analysis Population	L Pbla	
Listing 16.2.6.2	Assessment of Target Lesions	Full Analysis Population	L Tar	
Listing 16.2.6.3	Assessment of Non-Target Lesions	Full Analysis Population	L NTar	
	Enhancing Non Measurable Lesions	Full Analysis Population	L Enh	
Listing 16.2.6.4	Non-Enhancing Lesions	Full Analysis Population	L Nenh	
Listing 16.2.6.5	Evaluation of Overall Response	Full Analysis Population	L Tovr	
Listing 16.2.7.7	Dose Limiting Toxicities	Full Analysis Population	L Dlt	
Listing 16.2.7.1	Adverse Events	Full Analysis Population	L Ae	
Listing 16.2.7.2	Treatment Emergent Adverse Events	Full Analysis Population	L Ae	
Listing 16.2.7.3	Serious Adverse Events	Full Analysis Population	L Ae	
Listing 16.2.7.4	TEAEs leading to Study Drug Dose Modification	Full Analysis Population		
Listing 16.2.7.5	TEAEs leading to Study Discontinuation	Full Analysis Population	L Ae	
Listing 16.2.7.6	TEAEs with CTCAE Toxicity Grade ≥ 3	Full Analysis Population		
Listing 16.2.7.8	Deaths	Overall Safety Population	L Deat	
Listing 16.2.6.6	Survival	Full Analysis Population	L Surv	
Listing 16.2.6.7	Progression Free Survival Data	Full Analysis Population	L Pfs	
Listing 16.2.6.8	Kaplan Meier Survival and Censoring Times	Full Analysis Population	L Surv2	

Listing 16.2.8.5	SI Units and Conversion Factors	Full Analysis Population	L Conv	
Listing 16.2.8.1	Serum Chemistry Data	Full Analysis Population	L Labs	
Listing 16.2.8.2	Hematology and Coagulation Data	Full Analysis Population	L Labs	
Listing 16.2.8.3	Hematology and Coagulation Data	Full Analysis Population	L Labs	
Listing 16.2.8.4	Urinalysis Data	Full Analysis Population	L Labs	
Listing 16.2.9	Pregnancy Test	Full Analysis Population	L Preg	
Listing 16.2.10	Vital Signs	Full Analysis Population	L Vit	
Listing 16.2.11	ECG Data	Full Analysis Population	L Ecg	
Listing 16.2.12	Physical Examination	Full Analysis Population	L Phys	
Listing 16.2.13	Neurological Examination	Full Analysis Population	L Neuro	
Listing 16.2.14	Karnofsky Performance Status	Full Analysis Population	L Kps	
Listing 16.2.15	Visits	Full Analysis Population	L Vis	

Table/Figure Number	Table Title	Population	Tab Name		RAW	SDTM	ADaM	Table
Table 14.1.1	Subject Disposition	All Subjects	Disp			DS	ADSL	Disp table is done
Table 14.1.2	Protocol Deviations	Full Analysis Population	Dev			IE		
Table 14.1.3.1	Demography	Full Analysis Population	Demo		ENROLL/CDD/ HGGD/PBLES/ VS2	DM/DD/DS/ CM/ EX/QS	ADSL	Demo table is done
Table 14.1.3.2	Baseline Characteristics	Full Analysis Population	BasChar		ENROLL/CDD/ HGGD/PBLES/ VS2	DM/DD/DS/ CM/ EX/QS	ADSL	BasChar table is done
Table 14.1.4	Medical History	Full Analysis Population	Mhx			MH	ADMH	MHx table is done
Table 14.1.5	High Grade Glioma Diagnosis	Full Analysis Population	Diagh		ENROLL/CDD/ HGGD/PBLES/ VS2	DM/DD/DS/ CM/ EX/QS	ADSL	Diagh table is done
Table 14.1.6	Prior Cancer Treatments	Full Analysis Population	Canhist			CM/PR	ADCM	
Table 14.1.7	Previous Medications	Full Analysis Population	Meds			CM/PR	ADCM	
Table 14.1.8	Concomitant Medications	Full Analysis Population	Meds			CM/PR	ADCM	
Table 14.2	Best Overall Response	Per Protocol Population	BOR					
Table 14.2.1	Best Overall Response Concordance	Per Protocol Population	BORC					
Table 14.2.1.1	Objective Response Rate	Per Protocol Population	ORR					
Table 14.2.1.2	95% Confidence Intervals for Overall Response	Per Protocol Population	ORRci					
Table 14.2.2	Progression Free Survival	Per Protocol Population	PFS					
Table 14.2.3	Time to Overall Survival in Months	Per Protocol Population	OS			SS	ADTTE	
Table 14.2.3.1	OS for 20mg group 1 main study and 20 mg expansion for patients characteristics subgroups	Per Protocol Population	OSCAT					

Table 14.3.1.1	Overall TEAEs Summary	Full Analysis Population	AEoverall			AE	ADAE	AeOverall is done
Table 14.3.1.2	Treatment Emergent Adverse Events by System Organ Class and Preferred Term	Full Analysis Population	AEs			AE	ADAE	AEs tables are done
Table 14.3.1.3	Treatment-Related Adverse Events by System Organ Class and Preferred Term	Full Analysis Population	AEs			AE	ADAE	AEs tables are done
Table 14.3.1.4	Adverse Events Leading to Study Discontinuation by System Organ Class and Preferred Term	Full Analysis Population	AEs			AE	ADAE	AEs tables are done
Table 14.3.1.5	Adverse Events Leading to Discontinuation of Study Medication by System Organ Class and Preferred Term	Full Analysis Population	AEs			AE	ADAE	AEs tables are done
Table 14.3.1.6	Adverse Events Leading to Interruption of Study Medication by System Organ Class and Preferred Term	Full Analysis Population	AEs			AE	ADAE	AEs tables are done
Table 14.3.1.7	Adverse Events Leading to Dose Reduction of Study Medication by System Organ Class and Preferred Term	Full Analysis Population	AEs			AE	ADAE	AEs tables are done

Table 14.3.1.8	Adverse Events Leading to Death by System Organ Class and Preferred Term	Full Analysis Population	AEs			AE	ADAE	AEs tables are done
Table 14.3.1.9	Treatment Emergent Adverse Events by System Organ Class, Preferred Term and Severity	Full Analysis Population	AEs			AE	ADAE	AEs tables are done
Table 14.3.1.10	Treatment Emergent Adverse Events by System Organ Class, Preferred Term and Severity with CTCAE Toxicity Grade ≥ 3	Full Analysis Population	AESev			AE	ADAE	AESev tables are done
Table 14.3.1.11	Serious Adverse Events by System Organ Class and Preferred Term	Full Analysis Population	AESev			AE	ADAE	AESev tables are done
Table 14.3.1.12	Treatment Emergent Adverse Events by Preferred Term in Decreasing Frequency	Full Analysis Population	AEPT			AE	ADAE	AEPT tables are done
Table 14.3.1.13	Treatment-Related Treatment Emergent Adverse Events by Preferred Term in Decreasing Frequency	Full Analysis Population	AEPT			AE	ADAE	AEPT tables are done
Table 14.3.4.1	Listing of Abnormal Laboratory Values		Sig_lab		LAB_NORMLAB/ LBCHEM1/ LBCOAG1/ LBHEMA1/ LBTHYR/LBURIN1 /LBURIN2	LB	ADLB	
Table 14.3.4.2	Listing of Clinically Significant Laboratory Values		Sig_lab			LB	ADLB	
Table 14.3.5.1	Ad-RTS-hIL-12 Injections	Full Analysis Population	Exp1			EX/EC	ADEX	
Table 14.3.5.2	Veledimex Exposure	Full Analysis Population	Exp2			EX/EC	ADEX	
Table 14.3.5.3	Cemiplumab Exposure	Full Analysis Population	Exp3			EX/EC	ADEX	
Table 14.3.6.1	Summary of Serum Chemistry Results	Full Analysis Population	Lab			LB	ADLB	
Table 14.3.6.2	Clinical Significance of Serum Chemistry Results	Full Analysis Population	Lab2			LB	ADLB	
Table 14.3.6.3	Summary of Hematology Results	Full Analysis Population	Lab			LB	ADLB	
Table 14.3.6.4	Clinical Significance of Hematology Results	Full Analysis Population	Lab2			LB	ADLB	
Table 14.3.6.5	Summary of Coagulation Results	Full Analysis Population	Lab			LB	ADLB	
Table 14.3.6.6	Clinical Significance of Coagulation Results	Full Analysis Population	Lab2			LB	ADLB	
Table 14.3.6.7	Summary of Urinalysis Results	Full Analysis Population	Lab			LB	ADLB	
Table 14.3.6.8	Clinical Significance of Urinalysis Results	Full Analysis Population	Lab2			LB	ADLB	
Table 14.3.7	Summary of KPS	Full Analysis Population	KPS			QS	ADQS	
Table 14.3.8	Summary of Vital Signs	Full Analysis Population	Vitals					
Table 14.3.9	Summary of Weight	Full Analysis Population	Weight					
Table 14.3.10	Targeted Neurological Exam	Full Analysis Population	Neuro					
Table 14.3.11	ECG Findings	Full Analysis Population	ECG1			EG	ADEG	
Table 14.3.12	Summary of ECG Results	Full Analysis Population	ECG2			EG	ADEG	
Table 14.3.13	Dose Limiting Toxicities	Per Protocol Population	DLT					
Figure 14.2.3	Kaplan Meier plot of Progression Free Survival by Veledimex Dose							
Figure 14.2.4	Kaplan Meier plot of Overall Survival by Veledimex Dose							
Figure 14.2.5	Kaplan Meier plot of Progression Free Survival by Group							

Figure 14.2.6	Kaplan Meier plot of Overall Survival by Group						
Figure 14.2.7	Forest Plot	Per Protocol Population	FPLT				
Listing 16.2.1	Subject Disposition	Full Analysis Population	L_Disp				
Listing 16.2.3.1	Eligibility	Full Analysis Population	L_Elig				
Listing 16.2.3.2	Subject Population	Full Analysis Population	L_Pop				
Listing 16.2.2	Protocol Deviations	Full Analysis Population	L_Dev				
Listing 16.2.4.1	Demography and Baseline Characteristics	Full Analysis Population	L_Demo				
Listing 16.2.4.2	Medical and Surgical History	Full Analysis Population	L_Mhx				
Listing 16.2.4.3	High Grade Glioma Diagnosis	Full Analysis Population	L_Hgg				
Listing 16.2.4.4	Prior Cancer Treatment	Full Analysis Population	L_PriCnt				
Listing 16.2.4.5	Previous Medications	Full Analysis Population	L_Conm				
Listing 16.2.4.6	Concomitant Medications	Full Analysis Population	L_Conm				
Listing 16.2.4.7	Corticosteroid Dosage	Full Analysis Population	L_CDD				
Listing 16.2.4.8	Post Treatment Anti-Cancer Therapy	Full Analysis Population	L_PostCnt				
Listing 16.2.4.9	Concurrent Medical Procedures	Full Analysis Population	L_Npmcd				
Listing 16.2.5.1	Ad-RTS-hIL-12 Injection	Full Analysis Population	L_DS1				
Listing 16.2.5.2	Veledimex Capsule Diary	Full Analysis Population	L_DS2				
Listing 16.2.5.3	Veledimex Dose Modification	Full Analysis Population	L_DS3				
Listing 16.2.6.1	Pre-Baseline Lesion Assessment	Full Analysis Population	L_Pbla				
Listing 16.2.6.2	Assessment of Target Lesions	Full Analysis Population	L_Tar				
Listing 16.2.6.3	Assessment of Non-Target Lesions	Full Analysis Population	L_NTar				
Listing 16.2.6.4	Non-Enhancing Lesions	Full Analysis Population	L_Nenh				
Listing 16.2.6.5	Evaluation of Overall Response	Full Analysis Population	L_Tovr				
Listing 16.2.7.7	Dose Limiting Toxicities	Full Analysis Population	L_Dlt				
Listing 16.2.7.1	Adverse Events	Full Analysis Population	L_Ae				
Listing 16.2.7.2	Treatment Emergent Adverse Events	Full Analysis Population	L_Ae				
Listing 16.2.7.3	Serious Adverse Events	Full Analysis Population	L_Ae				
Listing 16.2.7.4	TEAEs leading to Study Drug Dose Modification	Full Analysis Population					
Listing 16.2.7.5	TEAEs leading to Study Discontinuation	Full Analysis Population	L_Ae				
Listing 16.2.7.6	TEAEs with CTCAE Toxicity Grade ≥ 3	Full Analysis Population					
Listing 16.2.7.8	Deaths	Overall Safety Population	L_Deat				
Listing 16.2.6.6	Survival	Full Analysis Population	L_Surv				
Listing 16.2.6.7	Progression Free Survival Data	Full Analysis Population	L_Pfs				
Listing 16.2.6.8	Kaplan Meier Survival and Censoring Times	Full Analysis Population	L_Surv2				
